8.2.4 Statistical Methods

Primary Safety

Incidence of adverse experiences will be descriptively summarized for all adverse experiences and Grade 3 or 4 adverse experiences separately. Summary statistics and plots will be generated for the change from baseline values in the vital signs, ECG parameters, and selected laboratory safety parameters for subjects, as deemed clinically appropriate. Depending on the safety parameter, the difference from baseline will either be computed on the original scale (raw change from baseline) or on the log scale and back-transformed for reporting (percent change from baseline). Summary statistics for the raw laboratory safety tests, ECGs, and/or vital signs may also be computed, as deemed clinically appropriate.

The incidence of intra- and postoperative complications will also be determined. Intra- and postoperative complications are not uncommon in patients undergoing surgical RCC resection, even in those proceeding directly to surgery without any neoadjuvant therapy. In a report of 58 such patients, the transfusion rate was 62.1% (median of 3.5 ± 6.6 units of blood products), and the complication rate was 27.6%, consisting of the need for surgical reexploration (5.2%), hospital readmission (8.6%), thromboembolic complications (1.7%), cardiovascular complications (3.4%), pulmonary complications (6.9%), gastrointestinal complications (10.3%), infectious complications (3.4%) and incision-related complications (6.9%) [79]. The incidence of surgical complications for patients receiving neoadjuvant MK-3475 will be summarized and contrasted with these published complication rates, as the total number subjects in this trial as well as the limited number of untreated controls will be of insufficient power to make accurate within study comparisons.

Primary PD

To assess the primary PD hypothesis, the posterior probability that the true response rate is at least 30% will be calculated based on a beta-binomial Bayesian model. A beta prior with parameters $\alpha=0.1$ and $\beta=0.1$ will be assumed. The primary PD hypothesis will be met with at least 80% posterior probability at interim analysis 1, at least 70% posterior probability at interim analysis 2, or at least 60% posterior probability at interim analysis 3. Additional sensitivity analyses may be performed where the definition of a responder is varied from 2-fold or greater increase in intratumoral lymphocytic infiltration to increases less than 2-fold.

Secondary PD

[REDACTED]

A two-sample t-test will be used to assess the difference in the expression of pretreatment tumor PD-1 ligands between immune cell infiltration responders and non-responders among patients receiving neoadjuvant MK-3475. If normality is not deemed tenable, data transformations will be considered, or a Wilcoxon rank sum test will be used. If enrollment of controls continues after the first interim analysis, similar analyses may also be done to compare patients receiving MK-3475 relative to controls.

Tertiary PD

[REDACTED]

[REDACTED]

[REDACTED] will be compared using a Bayesian model fit that has a fixed effect for method, and a random effect for patient to account for the within-patient correlation of measurements obtained from the same patient, using flat priors and an assumption of normality. If normality is not tenable, other distributions for the number of TILs may be considered. The posterior probability that the methylation approaches are within +/-10% of the ICH approach will be quantified. A posterior probability of 50% will satisfy this tertiary hypothesis.

Exploratory PD Objectives

Many of the exploratory PD objectives will be addressed using descriptive statistics, including:

- Differences in the IMR expression profiles between RCC tumor antigen-specific CD8+ T cells and unselected TILs in patients that are HLA-A2+
- Stimulation of antigen-specific anti-tumor immune responses in patients with RCC

Other exploratory objectives will be assessed using simple measures of association of potential biomarkers with immune infiltration (i.e., Pearson's or Spearman's correlation):

- Evaluate baseline as well as changes in serum/plasma levels of proteins, miRNAs, exosomes, nucleic acids, circulating antibodies, and other biomarkers after neoadjuvant MK-3475 therapy as potential biomarkers of the immune response to therapy
- Evaluate differences in tumor tissue miRNA expression levels in response to treatment with MK-3475
- Evaluate urine exosomes as a potential biomarker of immunologic response to neoadjuvant MK-3475 treatment
- Assess changes in RCC tumor tryptophan and arginine metabolism in response to MK-3475 treatment

The above objectives may also be assessed using a two-sample t-test to look at differences between immune infiltrate responders and non-responders. If normality is not deemed tenable, data transformations will be considered, or a Wilcoxon rank sum test may be used.

Two-sample t-tests will also be used to identify a possible correlation between clinical response and tumor immune cell infiltration by testing if the magnitude of immune cell infiltration differs between patients who have evidence of a clinical response versus those who do not among patients with metastatic disease. If normality is not deemed tenable, data transformations will be considered, or a Wilcoxon rank sum test may be used.

A paired t-test will be used to assess whether IMR ligand expression changes after treatment with MK-3475 in pre-treatment tumor biopsy tissue and resected tumor. If normality is not deemed tenable, data transformations will be considered, or a Wilcoxon signed rank test will be used.

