8.2.1 Hypotheses

Primary (Safety)

[figure not shown]
Neoadjuvant MK-3475 treatment will be well tolerated in patients undergoing subsequent surgical RCC tumor resection.

Primary (PD)

Neoadjuvant MK-3475 therapy will stimulate a 2-fold or greater increase in intratumoral lymphocytic infiltration in at least 30% of patients with RCC.

[figure not shown]
Secondary (PD)

1. 

Tertiary (PD)

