8.2.2 Analysis Endpoints

Primary Safety

The primary safety endpoints in this study include all types of adverse experiences, in addition to laboratory safety assessments, ECGs, and vital signs.

[figure not shown]
Primary PD

The primary PD endpoint in this study is the intratumoral lymphocytic infiltration in patients with RCC. Patients with at least a 2-fold increase in intratumoral lymphocytes will be considered immune cell infiltration responders.

Secondary PD

[figure not shown]

Tertiary PD

Exploratory PD

There are several exploratory endpoints in this study that include the following:

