8.2.5 Multiplicity

Since there is only one primary PD hypothesis, no multiplicity adjustment will be made when testing the primary hypothesis. The secondary and tertiary PD hypotheses will only be tested if the primary PD hypothesis is met. There are six separate secondary hypotheses and more than 8 tertiary hypotheses. Benjamini and Hochberg's false discovery rate multiplicity

adjustment will be applied at a rate of 10% when testing the secondary and tertiary hypotheses.

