| 35% | 25.5 | 50.1 | 67.5 |
| 40% | 39.2 | 69.3 | 84.8 |
| 45% | 53.6 | 83.7 | 94.6 |
| 50% | 68.7 | 92.8 | 98.5 |
| 55% | 82.0 | 97.5 | 99.8 |
| 60% | 90.1 | 99.2 | >99.9 |
| 65% | 95.3 | 99.8 | >99.9 |
| 70% | 98.3 | >99.9 | >99.9 |

IA = interim analysis

If the second interim analysis sample size is 12 (15) receiving neoadjuvant MK-3475, at least 80% posterior probability that the true immune cell infiltration response rate is 30% will be obtained if at least 6 (7) patients respond. If the third interim analysis sample size is 18 (24) receiving neoadjuvant MK-3475, at least 70% posterior probability that the true immune cell infiltration response rate is 30% will be obtained if at least 7 (9) patients respond. If the final analysis sample size is 24 (33) receiving neoadjuvant MK-3475, at least 60% posterior probability that the true immune cell infiltration response rate is 30% will be obtained if at least 6 (11) patients respond. Therefore, the analyses supporting the secondary and tertiary hypotheses will have as few as 6 responders.

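### The one visible secondary PD test uses only the 2-fold responder split, although fold change is measured on a continuous scale

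*Combined protocol and SAP*

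**What the plan says.** Section 8.2.2 sets the cut: "Patients with at least a 2-fold increase in intratumoral lymphocytes will be considered immune cell infiltration responders". Section 8.2.4 (Secondary PD) compares pretreatment PD-1 ligand expression across that cut among patients given neoadjuvant treatment: "A two-sample t-test will be used to assess the difference in the expression of pretreatment tumor PD-1 ligands between immune cell infiltration responders" and non-responders. If normality is doubtful, the data are transformed or a Wilcoxon rank-sum test is used. No analysis of this hypothesis on the fold change itself is visible.

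For several exploratory objectives the same section takes the other route: "Other exploratory objectives will be assessed using simple measures of association of potential biomarkers with immune infiltration", by Pearson or Spearman correlation. There the responder t-test is only optional.

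Section 8.2.5 adds a gate: "The secondary and tertiary PD hypotheses will only be tested if the primary PD hypothesis is met". It then applies Benjamini-Hochberg control at 10% to six secondary and more than 8 tertiary hypotheses. Section 8.2.7 accepts that "the analyses supporting the secondary and tertiary hypotheses will have as few as 6 responders". It gives no power for any secondary test.

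**The concern.** A patient at 1.9-fold is grouped with one at 0.5-fold, and a patient at 2.1-fold counts the same as one at 10-fold. The finer measure exists. Section 4.2.3.2 quantifies infiltration by immunohistochemistry, promoter methylation and TCR sequencing, and section 8.2.4 itself compares the magnitude of infiltration between clinical responders and non-responders. A secondary hypothesis therefore gets the coarser analysis while some exploratory ones get the finer one, and no reason is visible.

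At most 33 patients receive neoadjuvant treatment under the planned enrolment. Section 4.2.1.3 makes finding predictors of immune response a stated purpose of the trial. Information lost here cannot be recovered by enrolling a few more patients, and results for patients close to 2-fold depend on measurement error around the cut.

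**Working it through.** **Step 1: reproduce the plan's minimum of 6 responders.** Inputs are the Beta(0.1, 0.1) prior (8.2.4), the 30% target (8.2.1), and posterior cut-offs of 80%, 70% and 60% at the second interim, third interim and final analysis (8.2.6). Section 8.2.4 attaches these cut-offs to interims 1 to 3; the 8.2.6 version is used because it matches 8.2.7 and Table 14. With r responders among n treated, the quantity is P(p ≥ 0.30) under Beta(0.1 + r, 0.1 + n − r).

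| Analysis | n | Cut-off | One fewer responder | Minimum r | Plan says |
|---|---|---|---|---|---|
| Interim 2 | 12 | 80% | 5: 0.795 | 6: 0.924 | 6 |
| Interim 2 | 15 | 80% | 6: 0.785 | 7: 0.909 | 7 |
| Interim 3 | 18 | 70% | 6: 0.604 | 7: 0.780 | 7 |
| Interim 3 | 24 | 70% | 8: 0.624 | 9: 0.775 | 9 |
| Final | 24 | 60% | 7: 0.447 | 8: 0.624 | 6 |
| Final | 33 | 60% | 10: 0.501 | 11: 0.649 | 11 |

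Five of the six thresholds reproduce. Six of 24 has posterior probability 0.276 and fails the 60% rule; the final threshold should be 8. That is a separate slip. The overall minimum of 6 still stands, through 6 of 12.

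**Step 2: information kept by the split.** Assume log fold change is normal and linearly related to ligand expression. With responder share q and z the normal quantile at q, the asymptotic efficiency of the split relative to the continuous measure is φ(z)² / [q(1 − q)].

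- 6/12, q = 0.50: 0.3989² / 0.25 = 0.637, loss 36.3%
- 7/15: loss 36.5%
- 7/18: loss 38.2%
- 9/24: loss 38.7%
- 8/24 or 11/33, q = 0.333: 0.3636² / 0.2222 = 0.595, loss 40.5%
- q = 0.30 or 0.70: 0.3477² / 0.21 = 0.576, loss 42.4%

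The loss passes 40% only when q is below about 0.34 or above about 0.66. In patient terms, 33 × 0.595 = 19.6 and 12 × 0.637 = 7.6: the split uses 33 patients about as well as a continuous analysis uses 20, and 12 about as well as 8.

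Enumerating every path under the 8.2.6 rules that meets the primary hypothesis gives a mean loss of 38.2%, 37.9%, 38.0%, 38.4% and 40.9% at true response rates of 30%, 40%, 45%, 50% and 60%. The chance that the loss exceeds 40% is 21%, 14%, 15%, 21% and 44% respectively.

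**Step 3: power.** Under the same model, 20,000 simulated trials per setting treat the r largest fold changes as responders and compare the t-test with Pearson correlation at an unadjusted two-sided 5%. The correlation is assumed; three values show the range.

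| Responders/n | Correlation 0.3 | 0.5 | 0.6 |
|---|---|---|---|
| 6/12 | 11% vs 16% | 25% vs 40% | 35% vs 58% |
| 8/24 | 19% vs 30% | 47% vs 72% | 66% vs 90% |
| 11/33 | 25% vs 40% | 62% vs 87% | 82% vs 97% |

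The first figure in each cell is the t-test.

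**The case against.** The strongest reply is that these figures need a normal, linear model, and the plan's own rationale leans towards two groups. Section 4.2.1.5 cites a melanoma study in which CD8+ infiltrates rose more than 2-fold in most clinical responders and in no patient with progressive disease. Take such a scenario: 35% true responders, mean log2 fold change 0 or 2 with SD 0.5, and a ligand shift of 1.2 SD. The planned t-test then beats Pearson, at about 69% against 61-62% for n = 24 and 82% against 77% for n = 33. Spearman does worse, at 51% and 66%. This stands, but it depends on clean separation: with SD 1 the n = 24 figures are about 36% for the t-test and 38% for Pearson. It is a reason to keep the responder test, not to have it alone.

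The responder t-test also follows naturally from the primary endpoint. And section 8.2.4 allows sensitivity analyses with a cut below 2-fold, but these are optional, are written for the primary endpoint, and still dichotomise.

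The power figures are not on the plan's error scale. If the secondary and tertiary hypotheses are pooled (at least 6 + 9 = 15), the strictest Benjamini-Hochberg step is 0.10/15 = 0.0067. Both methods would lose power there, so the table shows the comparison, not the power the trial will have.

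A reader might infer that all six secondary tests rest on the split. Only one is visible; the methods for the others are redacted and cannot be judged.

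**Conclusion.** The point holds for the single visible secondary test. Under a normal, linear relation, comparing ligand expression only across the 2-fold cut loses about 36-42% of the information for responder shares of 30-70%. At an assumed correlation of 0.5 it costs roughly 15 to 25 percentage points of unadjusted power. The documents give neither the distribution of fold change nor a correlation, so both figures are conditional.

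Two stronger readings are tempting. One is a flat loss of more than 40%. At the smallest responder counts that open the gate, the loss runs from 36.3% to 40.5%, and at the only qualifying outcome with 6 responders (6 of 12) it is 36.3%. The other takes 6 of 24 from section 8.2.7 and reads off the loss of 46% for a 25/75 split. That outcome fails the plan's own 60% rule, so the secondary tests would not be run.

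Nor is the split the weaker method in every case, as the two-group scenario shows. This is a low-severity improvement in efficiency; the planned test is not invalid.

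**What to change.** In section 8.2.4, make correlation or linear regression of log2 fold change on pretreatment ligand expression the main analysis of this hypothesis, using the same infiltration measure that defines response. Use Spearman if normality fails, with the rule for switching stated in advance. Keep the two-sample t-test by responder status as a named supportive analysis, which covers the two-group case. Report mean log2 fold change with its 95% CI beside the responder rate. Leave the 2-fold definition, the primary analysis and the sample size unchanged.

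The cost is a few lines of SAP text, with no new samples, assays or patients. Section 8.2 already requires changes to the plan to be listed and explained. The change should be fixed before the secondary results are seen, so that the method is not chosen by outcome.

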5.3 Randomization or Treatment Allocation

Subjects will be assigned randomly according to a computer-generated allocation schedule.

The sample allocation schedule is shown in [Table 4](#).

Table 4 Sample Allocation Schedule

| Patients ^a | Treatment Group |
|-----------------------|--|
| n=24 | 200 mg MK-3475 Q3 weeks, 2 or 3 doses ^b |
| n=12 | Control |

^a Patients will be randomized to receive neoadjuvant MK-3475 or control. Allocation will be done in blocks of 3, ensuring 6 treated and 3 controls will be available for the first interim analysis. Depending on results of the first interim analysis, the control arm (and allocation numbers associated with the control arm) may be dropped from the allocation schedule, in which case patient numbers will be 33 and 3 for MK-3475 and controls, respectively.

^b Also depending on the results of the first interim analysis, the number of neoadjuvant doses of MK-3475 may be increased from 2 to 3.

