8.2.6 Interim Analysis

There will be up to 3 interim analyses done for this study. The first interim analysis will be performed after the initial 9 RCC patients, randomized 2:1 to either receive neoadjuvant MK-3475 vs. control (proceed to SOC RCC resection), have all undergone tumor resection and the assessment of tumor immune cell infiltrates has been completed. At the first interim analysis, the number of patients with an immune cell infiltration “response”, defined as a 2-fold or greater increase in the immune cell infiltrate in RCC tumor specimens compared with that in the pretreatment tumor biopsy specimens from the same patient, will be examined in the 6 patients receiving neoadjuvant MK-3475. If 4 or more of the first 6 patients receiving neoadjuvant MK-3475 respond, randomization will continue 2:1 to receive either neoadjuvant MK-3475 or control (proceed to SOC RCC resection), respectively, for the remainder of the study. If less than 4 of the first 6 patients receiving neoadjuvant MK-3475 respond, all subsequently enrolled patients may receive neoadjuvant MK-3475 with no further patients being randomized to the control group. Further, if there are 0 or 1 responders in the first 6 patients receiving neoadjuvant MK-3475, then the number of doses of MK-3475 that will be administered in patients subsequently enrolled may be increased from two to three (with the 200 mg dose and the Q3W dosing interval remaining the same). The probabilities of various outcomes after the first interim analysis are provided in [Table 12](#) below, assuming a true immune cell infiltration response rate of 5%, 30%, or 70%.

Table 12 First Interim Analysis Outcome Scenarios

Various outcomes after the first interim analysis assuming a true immune cell infiltration response rate of 5%, 30%, or 70%

| Outcome of first interim analysis | Action | Probability if true response rate = | | |
|-----------------------------------|--|-------------------------------------|-----|-----|
| | | 5% | 30% | 70% |
| 0-1 responders | Enroll all subsequent patient to MK-3475, increase from 2 to 3 doses | 97% | 42% | 1% |
| 2-3 responders | Enroll all subsequent patient to MK-3475, continue with 2 doses | 3% | 51% | 24% |
| 4-6 responders | Continue 2:1 randomization (MK-3475:Control) | < 1% | 7% | 74% |

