The second interim analysis will occur after a total of 18 RCC patients have undergone tumor resection, with either 15 receiving neoadjuvant MK-3475 with 3 controls or 12 receiving neoadjuvant MK-3475 with 6 controls. The primary PD hypothesis will be assessed, and success will be declared and enrollment may stop if there is at least 80% posterior probability that the true response rate is at least 30%. If success cannot be declared after the initial 18

patients, an additional 9 patients may be enrolled and randomized as determined by the results of the first interim analysis, and a third interim analysis will occur after 27 RCC patients have undergone tumor resection, with either 24 receiving neoadjuvant MK-3475 with 3 controls or 18 receiving neoadjuvant MK-3475 with 9 controls. The primary hypothesis will be assessed, and success will be declared and enrollment may stop if there is at least 70% posterior probability that the true response rate is at least 30%. If success cannot be declared after the initial 27 patients, an additional 9 patients may be enrolled and randomized as determined by the results of the first interim analysis. The final analysis will be performed after 36 RCC patients have undergone tumor resection. At the final analysis, success will be declared if there is at least 60% posterior probability that the true response rate is at least 30%.

After each interim analysis, decisions related to enrolling additional patients may deviate from the rules defined above based on the accumulating data, at the discretion of the Sponsor.

In addition, decisions related to stopping the study for futility may also be considered at each interim analysis. At the second interim analysis, if there are only 0 or 1 responders the study may be stopped for futility. The probability of this happening when the true response rate is 30% is 8.5% (3.5%) with a sample size of 12 (15). At the third interim analysis, if there are 2 or less responders the study may be stopped for futility. The probability of this happening when the true response rate is 30% is 6.0% (1.2%) with a sample size of 18 (24).

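### The optional MK-3475 versus control comparison follows, by default, from a high response in the first six treated patients, who are then counted in it; report it with and without the first cohort

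*Combined protocol and SAP*

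**What the plan says.** The comparison with controls appears under the secondary PD methods in Section 8.2.4, after a two-sample t-test of pretreatment PD-1 ligand expression in responders versus non-responders: "If enrollment of controls continues after the first interim analysis, similar analyses may also be done to compare patients receiving MK-3475 relative to controls".

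Section 8.2.6 decides whether controls continue: "If 4 or more of the first 6 patients receiving neoadjuvant MK-3475 respond, randomization will continue 2:1 to receive either neoadjuvant MK-3475 or control". Otherwise, "If less than 4 of the first 6 patients receiving neoadjuvant MK-3475 respond, all subsequently enrolled patients may receive neoadjuvant MK-3475". Section 5.3 (Table 4, note a) repeats the dependence: "Depending on results of the first interim analysis, the control arm (and allocation numbers associated with the control arm) may be dropped from the allocation". It also fixes the first cohort: "Allocation will be done in blocks of 3, ensuring 6 treated and 3 controls will be available for the first interim analysis".

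Later looks count cumulatively. The second interim takes place "with either 15 receiving neoadjuvant MK-3475 with 3 controls or 12 receiving neoadjuvant MK-3475 with 6 controls"; if controls continue, the third has 18 and 9 and the final analysis 24 and 12. Section 8.2.3 assigns all PD analyses to the Per-Protocol set. Neither that definition nor the visible text of 8.2.4 sets the first cohort apart.

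**The concern.** The decision to keep a control arm uses outcomes from the treated arm alone. When the default rule keeps it, the first six treated patients are known to have responded well, while the three controls randomised with them are an unselected sample. Pooling all of them into one comparison mixes a selected treated subgroup with unselected controls.

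This matters most where the arm contrast is the main evidence. Fresh-tissue TIL expression is collected only at resection (4.2.3.2), so it has no within-patient baseline and the randomised contrast carries the inference. The 10% false discovery rate procedure in 8.2.5 takes its p-values as valid and does not correct such a shift.

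**Working it through.** **Inputs from the plan.** First cohort 6 treated and 3 controls (5.3); controls continue at 4 or more of 6 (8.2.6); cumulative sizes 12/6, 18/9 and 24/12 (8.2.6, Table 4); hypothesised response rate 30% (8.2.1).

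**Assumptions.** A normally distributed marker with correlation ρ to the log fold change; responders are patients above the corresponding quantile of fold change; no arm difference in the marker; two-sided 5% t-test, so 2.5% in the upper tail. The plan gives neither a correlation nor a per-test level.

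**1. Reproduce Table 12.** With X ~ Bin(6, p), at p = 0.30:
P(X ≥ 4) = 15(0.3⁴)(0.7²) + 6(0.3⁵)(0.7) + 0.3⁶ = 0.0595 + 0.0102 + 0.0007 = 0.0705.
At p = 0.70 it is 0.744, and at p = 0.05 it is below 0.001. Table 12 gives 7%, 74% and below 1%.

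**2. The first six, given that controls continue.** At p = 0.30:
E[X | X ≥ 4] = (4 × 0.05954 + 5 × 0.01021 + 6 × 0.00073)/0.07047 = 4.166, a rate of 69.4%.
At p = 0.70 the rate is 78.7%.

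**3. Size of the shift.** For a standard normal fold change cut at its 70th percentile (0.524, density 0.348), the mean is 0.348/0.30 = 1.159 in responders and −0.348/0.70 = −0.497 in non-responders. The first six then average
0.694 × 1.159 − 0.306 × 0.497 = 0.653 SD.
The treated-arm shift for a marker with correlation ρ is ρ × 0.653 × 6/n:
- ρ = 0.5: 0.16 SD at n = 12, 0.08 SD at n = 24.
- ρ = 1.0: 0.33 SD at n = 12, 0.16 SD at n = 24.

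At p = 0.70 the first six average 0.787 × 0.497 − 0.213 × 1.159 = 0.144 SD, so even at ρ = 1.0 the shift is 0.07 SD (n = 12) or 0.04 SD (n = 24).

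**4. Upper-tail error.** Simulated t-tests with no arm difference, given X ≥ 4. Runs of 40,000 trials differ from one another by a few tenths of a point.

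| True rate | ρ | 12 vs 6 | 24 vs 12 |
|---|---|---|---|
| 30% | 0 | 2.6% | 2.5% |
| 30% | 0.5 | about 4.7% | about 4.0% |
| 30% | 1.0 | 7.6% to 7.9% | 5.6% to 5.8% |
| 70% | 0.5 to 1.0 | about 2.9% to 3.2% | about 2.8% to 3.1% |

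The excess is directional: at 30% and ρ = 0.5 the two-sided error is only 5.7% (12 vs 6) or 5.2% (24 vs 12).

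**5. Which correlation is plausible.** Controls are measured at resection, so the shared quantity is a resection level, whereas selection acts on the resection-to-pretreatment ratio. If the two log levels have equal variance and correlation r, the correlation of the resection level with the log fold change is (1 − r)/√(2(1 − r)) = √((1 − r)/2). That is 0.71 at r = 0 and 0.50 at r = 0.5. For r ≥ 0, ρ = 1.0 is therefore beyond reach even for infiltration itself.

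**6. Leaving out the first cohort.** With 18 vs 9, upper-tail error is 2.3% to 2.5% for every ρ from 0 to 1. The cost in standard error is:
- √[(1/18 + 1/9)/(1/24 + 1/12)] = 1.15 at 36 patients.
- √[(1/6 + 1/3)/(1/12 + 1/6)] = 1.41 if enrolment stops at the second interim.

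**The case against.** The strongest reply is that this is an optional secondary analysis in a Phase I trial, with endpoints that cannot be identified. The comparison only may be done, closing the control arm below 4 responders is also only permitted, and 8.2.6 lets the sponsor depart from the enrolment rules. Text around the sentence in 8.2.4 is redacted. The visible neighbouring analysis uses pretreatment tissue, for which controls have no scheduled biopsy (flow chart 6.2). All of this stands: the selection is the default path, not a certainty, and the affected markers are unknown.

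A second reply is that dropping the first cohort is a poor trade. On this path the second-interim success boundary of 6 of 12 is reached in 63%, 92% and 99% of trials at true rates of 30%, 50% and 70%. If enrolment then stops, only 6 versus 3 remain. At a 30% rate and ρ = 1.0, simulated mean squared error (in SD² units) is lower with the first nine patients kept: 0.33 against 0.50 (12 vs 6 against 6 vs 3), and 0.145 against 0.166 (24 vs 12 against 18 vs 9). This also stands, and it is why the restricted set should accompany the pooled result and not replace it.

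A reader might infer more than the documents support. The treated-arm response rate on this path averages (4.166 + 6 × 0.3)/12 = 49.7% or (4.166 + 18 × 0.3)/24 = 39.9% when the true rate is 30%. It is tempting to call that a 10 to 20 point bias against controls. But response is defined against the same patient's pretreatment biopsy, so controls have no response rate under the scheduled procedures; these figures describe the treated arm alone. Nor is the comparison bound to favour MK-3475: a marker negatively associated with fold change shifts downward, and an unrelated one does not move.

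**Conclusion.** The point holds as a modest, fixable weakness. Under the default rule, the comparison with controls is made after a high response in six treated patients who remain in it. At a true 30% rate and an assumed correlation of 0.5, this shifts an associated marker by about 0.16 SD (12 vs 6) or 0.08 SD (24 vs 12) and raises upper-tail error from an assumed 2.5% to about 4.7% or 4.0%. The ρ = 1.0 figures are an upper extreme.

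The problem is largest where the comparison is rarest: controls continue in 7% of trials at a 30% rate. At 70%, where they continue in 74%, the excess error is well under one percentage point.

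The result rests on the assumed correlation, the normal model, the assumed test level, and inclusion of the first six by default. The figures do not include the further selection from testing secondary hypotheses only once the primary PD hypothesis is met (8.2.5). The primary PD posterior is not affected by this point.

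**What to change.** Add to Section 8.2.4: any MK-3475 versus control comparison will be reported side by side (a) in all per-protocol patients, labelled as subject to selection by the first-interim rule, and (b) in patients randomised after the first interim analysis only; a difference seen only in (a) will not be read as a drug effect.

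The cost is one sentence and one extra table, with no new data. Column (b) is imprecise: its standard error is about 15% higher at 18 vs 9 and about 41% higher at 6 vs 3. It also does not remove bias from later success stopping. With stopping at 6 of 12 or 7 of 18, the response rate among treated patients enrolled after the first interim still averages 34.5% when the true rate is 30%. The label should say so.

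### The methylation-versus-IHC rule bounds only the average difference between methods, so it can be met while individual patients disagree substantially

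*Combined protocol and SAP*

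**What the plan says.** In Section 8.2.4, under Tertiary PD, the methods "will be compared using a Bayesian model fit that has a fixed effect for method, and a random effect for patient"; the patient effect is there to handle correlation between measurements from the same patient. The fit is made "using flat priors and an assumption of normality", with a fallback: "If normality is not tenable, other distributions for the number of TILs may be considered". The criterion is "The posterior probability that the methylation approaches are within +/-10% of the ICH approach will be quantified", and the bar is "A posterior probability of 50% will satisfy this tertiary hypothesis".

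Three other places bear on it. Section 4.2.3.2 lists IHC, promoter methylation and TCR sequencing as ways of assessing infiltration. Section 8.2.6 works with a per-patient response, "defined as a 2-fold or greater increase in the immune cell infiltrate in RCC tumor specimens" relative to the same patient's pretreatment biopsy. Section 8.2.5 allows tertiary hypotheses to be tested only if the primary PD hypothesis is met.

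The tertiary objectives, hypothesis wording and endpoints, and the words leading into this analysis, are blacked out.

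**The concern.** The visible model has one parameter that compares the methods: the fixed method effect, which is the mean difference across patients. Patients in whom methylation reads high offset those in whom it reads low. Patient-by-patient disagreement goes into the residual, and no visible sentence limits it. The random patient effect does not help, because it removes the patient's overall level and does not test agreement within a patient.

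Two methods can therefore agree closely on average and still give very different values in the same patient. Infiltration is used in this trial patient by patient, so a statement that the methods agree would be read as applying to individuals. The planned rule would not support that reading. Raising the 50% bar makes the rule stricter, but the quantity tested remains mean bias.

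**Working it through.** **No figure to reproduce.** The SAP gives no sample size, power or error rate for this rule.

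**Inputs from the plan.** Margin ±10%, that is ln 0.9 = -0.105 to ln 1.1 = 0.095 on the log scale; bar 50%; flat priors; normality (Section 8.2.4). Treated patients number 12 or 15 at the second interim analysis, 18 or 24 at the third, and 24 or 33 at the end ("If the final analysis sample size is 24 (33) receiving neoadjuvant MK-3475", Section 8.2.7). All 36 patients, controls included, should have a resection specimen. The visible text does not say which of these sets enters the comparison.

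**Assumptions.** Paired differences are normal on the log scale with SD s, and the observed mean difference is zero. The plan states neither the scale nor the SD.

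**Formulas.**
- Posterior of the mean log ratio, with s taken as known: normal, mean 0, SD s/√n.
- Probability within ±10%: Φ(0.095/(s/√n)) - Φ(-0.105/(s/√n)).
- Share of patients more than two-fold apart: 2 × [1 - Φ(ln 2/s)].
- 95% limits of agreement: ×/÷ exp(1.96 s).

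**Moderate scatter, s = 0.5.**

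| n | s/√n | Posterior within ±10% | Rule met |
|---|---|---|---|
| 15 | 0.129 | 0.56 | yes |
| 24 | 0.102 | 0.67 | yes |
| 33 | 0.087 | 0.75 | yes |

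Share more than two-fold apart: 2 × [1 - Φ(0.693/0.5)] = 2 × [1 - Φ(1.386)] = 17%. Limits of agreement: ×/÷ exp(0.98) = 2.7. At s = 0.3 the share is 2%.

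**Large scatter, s = 0.8.** The posterior is 0.53 at n=33 (met) and 0.46 at n=24 (not met). The share more than two-fold apart is 39%, with limits ×/÷ 4.8.

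**Largest s that still passes.** This solves posterior = 0.50 using a t posterior with n-1 degrees of freedom, which allows for s being estimated.

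| n | Largest s | Share more than two-fold apart |
|---|---|---|
| 12 | 0.50 | 16% |
| 15 | 0.56 | 22% |
| 18 | 0.62 | 26% |
| 24 | 0.72 | 33% |
| 33 | 0.84 | 41% |
| 36 | 0.88 | 43% |

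If the observed mean is 5% off zero, the shares fall to 30% (n=24), 38% (n=33) and 40% (n=36).

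**How often such a case would pass.** These are simulations with no true mean difference.
- One third of patients more than two-fold apart: the rule is met in 17% (n=24), 40% (n=33) and 46% (n=36) of trials.
- s = 0.8: it is met in 7% (n=24) and 23% (n=33).
- Raw-scale analysis, one third more than two-fold apart, between-patient CV assumed 0.5 or 1.0: 8-11% (n=24), 15-24% (n=33) and 18-28% (n=36).

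**Effect of the bar.** With the known-s formula and an observed mean of zero, an 80% bar caps the share more than two-fold apart at 7% (n=24) or 12% (n=33). A 95% bar caps it at 0.6% or 1.8%.

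**The other reading of the same sentence.** If ±10% and 50% applied to one patient's ratio, s would have to be about 0.15 or less. At n=33 the mean-based reading tolerates 0.84, which is 0.84/0.15 = 5.6 times as much.

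**The case against.** The strongest reply starts from the redactions. The hypothesis itself is hidden. If it concerns average equivalence, the analysis fits it, and a patient-level summary may sit in the blacked-out text. The criterion sentence does not name the mean either; that is inferred from the model. This stands as a limit on what can be claimed. It does not remove the need to say which quantity must lie within ±10%, because the two readings differ so much.

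Three stronger conclusions that a reader might draw are not supported:

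- **That more than a third of patients would typically disagree two-fold when the rule is met.** This needs an assumed SD near 0.8, an observed mean difference of about zero and roughly 33-36 patients. At SD 0.8 and n=24 the rule is not met, and in simulation it usually fails even at n=33. Having 33 treated patients also requires that controls were dropped after the first interim analysis and that enrolment ran to 36.
- **That these shares are rates of discordant response calls.** The response is a ratio of resection to biopsy in the same patient. An offset between methods that is constant within a patient cancels from that ratio.
- **That methylation decides the two-fold call or is to replace IHC.** Section 8.2.2 and Section 8.2.6 define the responder without naming an assay, and no visible text announces a replacement.

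It is also fair that much of the looseness in the limiting figures comes from the 50% bar. What stands apart from the bar is that mean bias is the only thing tested.

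**Conclusion.** The point holds within those limits. On the visible text, a 50% posterior probability about the mean method difference is sufficient, so the hypothesis can be met with substantial disagreement in individual patients: about 17% more than two-fold apart at an assumed log-scale SD of 0.5 with 15 to 33 patients. The upper limits of 16-26% (n=12-18), 33% (n=24) and 41-43% (n=33-36) show what the rule tolerates. They are not forecasts, since they rest on normal log ratios, an observed mean difference of zero and an SD the plan does not give.

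The consequence is confined to one of more than eight tertiary hypotheses. No visible interim rule and no primary conclusion depends on it.

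**What to change.** In Section 8.2.4:

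1. State that the ±10% criterion refers to the mean method difference, and report it as bias only. State the analysis scale, and correct ICH to IHC if that is what is meant.
2. From the same model and data, add the Bland-Altman 95% limits of agreement on the scale analysed, the concordance correlation, and the posterior predictive probability that one patient's methylation value lies within a pre-stated margin of IHC.
3. Where biopsy and resection are both measured by both methods, add the proportion of patients given the same two-fold call.
4. Conclude agreement between methods only if the patient-level criterion is also met, with its margin and pass level fixed before analysis. Carrying over ±10% and 50% unchanged would require an SD of about 0.15 or less, so the margin should be chosen deliberately.

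The cost is SAP wording and a few lines of analysis, with no new samples. The downside is that the tertiary hypothesis becomes harder to meet. If the redacted text already holds a patient-level summary, it need only be tied to the conclusion as in step 4.
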